## Background

Surgery can be a serious mental strain for the patient and can result in anxiety [1]. Anxiety is usually treated with benzodiazepines which have unpleasant adverse effects and can lead to serious complications [2,3].

Melatonin is a naturally occurring hormone which has documented anxiolytic effects in both experimental and clinical studies [4-7]. Melatonin does not have any known serious adverse effects [8], and the known adverse effects are dizziness, headache, nausea, and fatigue. Melatonin could potentially be an effective anxiolytic drug for treating perioperative anxiety [9].

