## Objective

To investigate the effect of oral melatonin on perioperative anxiety.

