## Study design

Randomized, double-blinded, placebo-controlled trial involving patients undergoing elective inguinal/umbilical hernia repair. Outcomes of interest are anxiety, well-being, and sleep quality. Participants will be allocated to either melatonin or placebo in a 1:1 ratio and will be randomized in blocks of 4.

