### *Fatigue and well-being*

Subjective fatigue will be measured on a 10-point scale (higher score indicates more fatigue). Well-being will be measured using a VAS (higher score indicates less well-being). Will be administered on the morning before and after surgery.

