## Ethical considerations

This trial will be conducted in accordance with the Helsinki Declaration and with the permission of the Medical Ethics Committee of the Capital Region of Denmark. The study will contribute to the understanding of melatonin's anxiolytic

benefits and will be conducted using a randomized double-blinded design. The safety of oral administration of melatonin is well-established [13-27]. All participants will give written and verbal informed consent to participate. Participants can withdraw from the trial at any timepoint.

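### This abbreviated protocol names four known adverse effects of melatonin but plans to measure only fatigue, so no systematic between-arm data on dizziness, headache or nausea are planned.

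*Combined protocol and SAP*

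**What the plan says.** The Background sets the drawbacks of current treatment beside the profile of melatonin. On current treatment: "Anxiety is usually treated with benzodiazepines which have unpleasant adverse effects and can lead to serious complications". On melatonin: "Melatonin does not have any known serious adverse effects", followed by the statement that "the known adverse effects are dizziness, headache, nausea, and fatigue". The same section also rests on efficacy, describing melatonin as a hormone "which has documented anxiolytic effects in both experimental and clinical studies".

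The Objective is a single sentence: "To investigate the effect of oral melatonin on perioperative anxiety". The Study design section adds: "Outcomes of interest are anxiety, well-being, and sleep quality".

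The Outcomes section lists one primary and ten secondary outcomes. Fatigue is among them. Dizziness, headache, nausea and adverse events are not. In the measurement sections, fatigue has its own scale: "Subjective fatigue will be measured on a 10-point scale (higher score indicates more fatigue". The other instruments cover anxiety (STAI and VAS), sleep quality, sleepiness (Karolinska scale) and well-being (VAS). The Statistics section names a test for level of anxiety only.

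Ethical considerations relies on earlier literature: "The safety of oral administration of melatonin is well-established". The closing statement after the reference list says that the document is a shortened translation of the approved protocol and that the trial follows ICH-GCP and applicable legislation.

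**The concern.** A plan that names four expected effects of its drug would normally ask about all four, in both arms, at fixed times. This document does so for one. Symptoms that nobody asks about at the scheduled contacts cannot be recovered later, so the gap cannot be repaired at the analysis stage.

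Two features of the setting add to this. First, dizziness, headache and nausea can also follow anaesthesia and opioids, and the trial records propofol, remifentanil and rescue opioid as outcomes. Spontaneous postoperative reports would therefore carry a background unrelated to the tablets. Second, the schedule already contains a contact that avoids most of that background, the anxiety assessment 60 minutes before surgery, and the plan does not use it for this purpose.

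At stake is the harms side of the report. A favourable anxiety result would stand beside data on fatigue, sleepiness and general well-being, but without a systematic count of three effects that the protocol itself expects.

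**Working it through.** **Named against measured**

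| Effect named in Background | Listed outcome | Instrument |
|---|---|---|
| Dizziness | no | none |
| Headache | no | none |
| Nausea | no | none |
| Fatigue | yes (secondary) | 10-point scale, mornings before and after surgery |

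Four are named, one is measured, and 4 − 1 = 3 have no planned measurement. The well-being VAS may move with any of the three but identifies none of them.

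**Contacts against tablets** (Study course; measurement sections). Tablets of 10 mg or placebo are given at 9 pm the evening before surgery, 120 minutes before surgery, directly after surgery, and at 9 pm that day. In the melatonin arm this is 4 × 10 = 40 mg over 24 hours.

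| Existing contact | Tablets taken | Anaesthesia yet? |
|---|---|---|
| Recruitment | 0 | no |
| 60 minutes before surgery | 2 (the second 120 − 60 = 60 minutes earlier) | no |
| 4 hours after surgery | 3 | yes |
| Morning after surgery | 4 | yes |

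**The plan's own sample size** (Power and sample size: difference 10, SD 10.0, power 0.80, 5%, taken as two-sided). n per arm = 2 × (1.960 + 0.842)² × (10/10)² = 15.7, rounded up to 16. The stated figure is reproduced. No allowance for drop-out is stated.

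**What 16 per arm can show.** The documents give no rates for these effects, so every rate below is an assumption.

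Chance of seeing at least one case among 16 = 1 − (1 − p)^16. The last column assumes that only half of cases are volunteered, so p is halved.

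| Assumed true rate p | All 16 asked | Half of cases volunteered |
|---|---|---|
| 5% | 1 − 0.95^16 = 0.56 | 1 − 0.975^16 = 0.33 |
| 10% | 1 − 0.90^16 = 0.81 | 1 − 0.95^16 = 0.56 |
| 20% | 1 − 0.80^16 = 0.97 | 1 − 0.90^16 = 0.81 |

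If all 16 are asked and none reports the symptom, the exact (Clopper-Pearson) two-sided 95% upper limit is 1 − 0.025^(1/16) = 0.206, about 21%.

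Power for a formal comparison, 16 against 16, two-sided 5%:

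| Assumed rates | Normal approximation | Fisher exact | n per arm for 80% power (normal) |
|---|---|---|---|
| 10% vs 20% | 0.12 | 0.05 | 199 |
| 10% vs 30% | 0.29 | 0.17 | 62 |
| 10% vs 40% | 0.50 | 0.36 | 32 |
| 10% vs 50% | 0.71 | 0.58 | 20 |

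With 0 of 16 in one arm, at least 5 of 16 are needed in the other for a Fisher p value of 0.05 or less. A test would be uninformative unless the difference were very large, so the data are useful for description only.

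**The case against.** The strongest reply is that absence from this document is not absence from the trial. It is a shortened translation, run under ICH-GCP with medicines-agency permission, and safety procedures may be among the text left out. This stands: a reader might infer that the trial cannot compare these effects at all, and the documents do not support that. What can be said is that this version describes no collection of them. A general ICH-GCP commitment would bring in reported events, but it does not by itself establish that named symptoms are asked about at fixed times in both arms.

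A reader might also infer that tolerability is the reason for testing melatonin. The documents do not go that far. The only objective is anxiety, the Background also argues from efficacy, and safety is treated as already established. Tolerability relative to benzodiazepines is one strand of the rationale. Because the comparator is placebo, even complete symptom data could not show an advantage over benzodiazepines.

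Third, 16 per arm is too few for a comparison of symptom rates. This stands for testing, as the power table shows. It does not remove the value of a complete count with an interval.

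Finally, with double blinding and identical tablets, symptoms due to surgery are expected in both arms, so counts by arm need no causal attribution. This also stands, and it would be conjecture to say that staff would ascribe such events to the operation. What remains is that a shared background and incomplete reporting make an effect of the tablets harder to see, and the 60-minute contact reduces the first of these.

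**Conclusion.** The point holds in a limited form. As published, the plan gives a measurement to one of the four adverse effects it names and provides no systematic between-arm data on the other three. The conclusion assumes that the full protocol does not already contain such questioning, which these documents cannot settle.

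The primary outcome, its analysis and the sample size are unaffected. The loss is descriptive. At an assumed 10% rate, the chance of seeing any case in an arm of 16 is 81% if everyone is asked and 56% if half of cases are volunteered; both figures move with the assumed rates. Even a clean count of 0 of 16 would be compatible with a true rate of up to about 21%, so collecting the data would not by itself justify calling melatonin well tolerated. This is a worthwhile, cheap improvement, not a flaw that undermines the trial's stated objective.

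**What to change.** Check the full protocol first. If it already asks about these symptoms at fixed times, state this in the public version. Otherwise:

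- Add dizziness, headache and nausea as three fixed items to the existing REDCap forms at recruitment (before any tablet), 60 minutes before surgery, 4 hours after surgery and the morning after surgery.
- List the checklist as a secondary safety outcome.
- For each symptom and contact, report the number affected out of the number asked, by arm, with exact 95% intervals and no hypothesis test.
- Highlight the 60-minute reading as the one taken after two tablets and before anaesthesia, with the recruitment reading beside it.
- State in the plan that 16 per arm supports description only, and that placebo control allows no tolerability claim against benzodiazepines.

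The cost is three short items at each of four existing contacts (3 × 4 = 12 answers per patient) and one extra results table. No visit, treatment or sample size changes.

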## Objective

To investigate the effect of oral melatonin on perioperative anxiety.

## Study design

Randomized, double-blinded, placebo-controlled trial involving patients undergoing elective inguinal/umbilical hernia repair. Outcomes of interest are anxiety, well-being, and sleep quality. Participants will be allocated to either melatonin or placebo in a 1:1 ratio and will be randomized in blocks of 4.

## Participants

Inclusion criteria:

- Male patients undergoing elective inguinal or umbilical repair.

Exclusion criteria:

- Patients with regular consumption of opioids, benzodiazepines, or melatonin.
- Patients with psychiatric comorbidity (ongoing treatment) or patients classified as ASA 3 or 4
- Patients with an ongoing abuse of alcohol or recreational drugs'
- Patients suffering from liver disease (ongoing treatment)'
- Patient diagnosed with a sleeping disorder
- Allergy towards melatonin
- Patients incapable of participating in accordance with the study protocol

Withdrawal and drop-out-criteria

1. If the participant wishes to withdraw from the trial at any timepoint
2. If the participant suffers from any treatment complication resulting in a reoperation or admission to an intensive care unit
3. If circumstances not covered by criteria 1-2 occur and the investigator deems it necessary in regard to the health of the participant

## Study course

Participants will be recruited according to the above criteria by study personnel after their preoperative consultation with the surgeon. Patients are given written and verbal information about the purpose and conduct of the study, and are required to give written and verbal consent to participate. Baseline data are collected.

Participants will be administered oral 10 mg melatonin at four different timepoints: at 9 pm the evening before surgery, 120 minutes before surgery, immediately after surgery, and at 9 pm the evening on the day of surgery.

Anxiety will be measured at different timepoint using both the State-Trait Anxiety Inventory (STAI) [10] and visual analogue scales (VAS). All data will be collected electronically using the platform Research Electronic Data Capture (REDCap).

## Pharmacology

Pharmaceuticals are produced and packaged according to Good Manufacturing Practice guidelines by and authorized manufacturer. The applied drugs are tablets containing 10 mg melatonin or placebo. Tablet are identical in size, shape, color, and flavor. Labelling is performed by the manufacturer in accordance with Good Manufacturing Practice guidelines.

## Randomization

Randomization, blinding, and labelling is performed by the authorized manufacturer. Randomization is performed trough Randomization.com using the first generator functionality. Participants are randomized in blocks of 4 and in a ratio of 1:1. The investigator are not aware of the content of the tablets. An identification key is stored in sealed envelopes.

## OUTCOMES

### *Primary outcomes*

- Preoperative anxiety 1 hour before surgery using STAI [10]

### *Secondary outcomes*

- Postoperative anxiety using STAI [10]
- Pre- and postoperative anxiety using VAS
- Length of stay
- Quality of sleep the night before and after surgery
- Intraoperative use of remifentanil
- Intraoperative use of propofol
- Use of rescue-opioid (0-6 hours postoperatively)

- Use of rescue-opioid (0-24 hours postoperatively)
- General well-being
- Fatigue

## MÅLINGER

### *Perioperative anxiety*

Perioperative anxiety is measured using both STAI and VAS at recruitment, 60 minutes before surgery, and 4 hours after surgery.

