## Statistics

Level of anxiety will be compared using Mann-Whitney's test or unpaired T test depending on the distribution of data. Data will be analyzed using Graphpad Prism (Graphpad Software, La Jolla, CA) and/or SPSS (IBM SPSS, Statistics for Windows, Version 20.0, Armonk, NY, IBM Corp). A p value of 0.05 will be considered significant. Data will be reported as mean (SD) or median (IQR) depending on distribution.

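### The only scheduled pre-dose anxiety score is taken at recruitment, an unstated time before surgery, and the planned test adjusts for no baseline: the comparison is valid but may lose precision

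*Combined protocol and SAP*

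**What the plan says.** On measurement, the section on perioperative anxiety gives three times: "Perioperative anxiety is measured using both STAI and VAS at recruitment, 60 minutes before surgery, and 4 hours after surgery".

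On recruitment, the Study course section states: "Participants will be recruited according to the above criteria by study personnel after their preoperative consultation with the surgeon". It adds "Baseline data are collected" without listing the content. Neither section says how long before the elective operation this happens.

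On dosing, the same section places the tablets "at 9 pm the evening before surgery, 120 minutes before surgery, immediately after surgery, and at 9 pm the evening on the day of surgery".

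The primary outcome is "Preoperative anxiety 1 hour before surgery using STAI". The analysis is given in the Statistics section: "Level of anxiety will be compared using Mann-Whitney's test or unpaired T test depending on the distribution of data". No baseline covariate or change score is mentioned there, and the section on power and sample size uses no baseline value.

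**The concern.** In time order, the schedule is: recruitment (first anxiety score), first tablet, second tablet, 60-minute score, surgery, 4-hour score. Two doses precede the primary measurement, and nothing ties the single untreated score to the days or hours before the operation.

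The trial studies anxiety around surgery. A score from a clinic contact some time earlier may or may not reflect how anxious a participant is just before the first tablet. If it does not, it explains little of the variation in the 60-minute STAI and gives a poor picture of whether the arms were alike in anxiety when treatment began. The plan also names no use for the score in the analysis, so even a good baseline would add nothing to the primary comparison as written.

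At stake is the width of the confidence interval in a trial of 32 participants, for which the documents state no allowance for drop-out.

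**Working it through.** **Inputs.** From the section on power and sample size: difference 10 points, SD 10.0, power 0.80, significance level 5%, 16 per group. Sidedness is not stated; two-sided testing reproduces the sample size, whereas one-sided testing would give 13. The correlation r between the pre-dose score and the 60-minute STAI appears nowhere in the documents and is varied below as an assumption.

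**Step 1: the plan's own figure.** n per group = 2(1.960 + 0.842)² × (10/10)² = 15.70, rounded up to 16. The stated number is reproduced. It comes from the normal approximation, under which power at 16 is 0.807.

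**Step 2: the planned test.** The standard error of the difference is 10 × √(2/16) = 3.54. The noncentrality is 10/3.54 = 2.83 on 30 degrees of freedom, so exact t-test power is 0.781. The 95% CI half-width is 2.042 × 3.54 = 7.22 points. Neither figure depends on r, because the test uses no baseline.

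**Step 3: baseline-adjusted analysis.** Residual SD = 10 × √(1 − r²), with 29 degrees of freedom and t quantile 2.045. The half-width is 2.045 × residual SD × √(2/16).

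| r (assumed) | Residual SD | Power | CI half-width (points) |
|---|---|---|---|
| 0 | 10.00 | 0.780 | 7.23 |
| 0.2 | 9.80 | 0.797 | 7.08 |
| 0.3 | 9.54 | 0.817 | 6.90 |
| 0.4 | 9.17 | 0.847 | 6.63 |
| 0.5 | 8.66 | 0.884 | 6.26 |
| 0.6 | 8.00 | 0.927 | 5.78 |
| 0.7 | 7.14 | 0.969 | 5.16 |

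**Step 4: a refinement for small samples.** Step 3 treats the arms as exactly balanced on the covariate. With a normally distributed covariate, chance imbalance multiplies the variance by about 1 + 1/(32 − 4) = 1.036. Power then becomes 0.766 at r = 0, 0.783 at r = 0.2, 0.834 at r = 0.4, 0.873 at r = 0.5 and 0.964 at r = 0.7. A simulation of ANCOVA at this sample size agrees with these to within 0.005. Adjustment therefore breaks even with the unadjusted 0.781 at about r = 0.2 and gains above that.

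**Step 5: a change score is not a substitute.** Assuming equal SDs at both times, its SD is 10 × √(2(1 − r)). At r = 0.3 this is 11.83, with power 0.667 by the normal approximation, below the 0.807 of the unadjusted test. At r = 0.5 the two are equal. With r unknown, ANCOVA is the safer use of the baseline.

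**The case against.** The strongest reply is that nothing in the planned analysis depends on a baseline. Allocation is 1:1 in blocks of 4 with an identical placebo, the primary comparison is a randomised contrast at 60 minutes, and the sample size was set without a baseline. A weak or distant baseline costs this test no power. Chance imbalance is already in its standard error: with SE 3.54, a difference of 5 points or more between arms arises by chance in about 16% of randomisations (5/3.54 = 1.41 SE), and the test allows for that. All of this stands.

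A reader might infer two stronger claims. One is that no pre-dose score is taken near surgery. The documents do not show this. The interval is unstated, could be short, and may be given in the full protocol, since this document describes itself as an abbreviated translation. The other is that the recruitment score predicts the 60-minute score poorly. No correlation is reported, and the same instrument is used at both times. The documents also do not say whether the state or the trait part of the STAI is meant, and that would affect r.

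It is also fair to say that the extra form brings no power by itself. The gain needs a change of analysis, and how much the evening score adds over the recruitment score rests on assumed values. If r were 0.4 at recruitment and 0.5 on the evening before, power would rise only from 0.847 to 0.884. If the two correlations were equal, nothing would be gained.

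What survives is narrower. Proximity of the only untreated score to surgery is not secured, its use in the analysis is not stated, and both can be put right cheaply.

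**Conclusion.** The point holds as one about efficiency, not validity. The plan schedules a single pre-dose anxiety score, at an unspecified distance from surgery, and makes no stated use of it. The planned test is unbiased; its exact power of 0.781 is slightly under the target of 0.80. Baseline adjustment would bring power to about 0.85 at r = 0.4 and 0.97 at r = 0.7, and narrow the CI half-width from 7.22 to 6.63 and 5.16 points. At r = 0.2 or below the gain is nil, and at r = 0 adjustment costs about 1.5 percentage points of power (0.781 against 0.766 in Step 4).

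These figures assume the plan's difference and SD, two-sided testing, complete data, normally distributed scores and a linear relation with baseline. The value of r is an assumption throughout. The documents do not support saying that the baseline is taken at the wrong moment or that it predicts poorly. They support saying only that the plan does not guarantee a proximate pre-dose score.

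**What to change.** 1. **Statistics section.** Analyse the 60-minute and 4-hour STAI and VAS by ANCOVA, with treatment and the pre-dose score of the same scale as terms, and report the adjusted difference with its 95% CI. This replaces the choice between the two unadjusted tests for these outcomes; an unadjusted comparison can stay as a sensitivity analysis. The recruitment score is already collected, so this step needs no new data.
2. **Section on perioperative anxiety.** Add one short STAI and VAS form in REDCap, completed immediately before the tablet on the evening before surgery, and name it as the covariate. Keep the recruitment score as a second covariate, or use it to impute a missing evening score. Do not substitute it one-for-one, because that would mix two occasions with possibly different means and slopes in one covariate. Choose between these options before unblinding.
3. **Study course section.** State the expected interval from recruitment to surgery.

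The cost is one extra short form per participant, a few sentences of text and some missing evening forms. No additional patients are needed. If the evening score proves no better correlated than the recruitment score, only that form is lost.

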### *Sleep quality*

Quality of sleep is measured using a VAS where higher score equals better quality of sleep. Data on length of sleep and number of awakenings will also be collected.

### *Karolinska sleepiness scale*

This is a 9-point interval scale (1 = very awake; 9 = very sleepy) used to measure the degree of sleepiness. Will be administered on the morning before and after surgery.

### *Fatigue and well-being*

Subjective fatigue will be measured on a 10-point scale (higher score indicates more fatigue). Well-being will be measured using a VAS (higher score indicates less well-being). Will be administered on the morning before and after surgery.

## Power and sample size

The primary outcome is preoperative anxiety measured using STAI. A previous study investigated anxiety in relation to inguinal hernia surgery and found a mean preoperative STAI of 35.4 (SD 10.0) [11]. There are no generally agreed recommendation for what constitutes a clinically significant change on the STAI, but a change of one SD has been proposed [12]. In the current study, this equals a minimal relevant difference (MIREDF) of 10 points in the STAI or 28%. Necessary power is set at 0.80 and level of significance at 5%. This results in a necessary sample size of 16 participants in each group.

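### The recruitment STAI is collected before dosing but not named in the analysis; adjusting for it could add precision at no extra enrolment, and the stated power of 0.80 is about 0.78 for the planned t test

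*Combined protocol and SAP*

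**What the plan says.** Under Primary outcomes the endpoint is "Preoperative anxiety 1 hour before surgery using STAI". Under Perioperative anxiety the schedule is: "Perioperative anxiety is measured using both STAI and VAS at recruitment, 60 minutes before surgery, and 4 hours after surgery". Study course places recruitment after the preoperative consultation, adds "Baseline data are collected", and puts the first tablet on the evening before surgery. The recruitment STAI is therefore a pre-treatment measurement on the same scale as the primary outcome.

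The Statistics section says: "Level of anxiety will be compared using Mann-Whitney's test or unpaired T test depending on the distribution of data". It adds "A p value of 0.05 will be considered significant" and mentions no covariate and no change from baseline.

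Power and sample size takes its spread from an earlier study that "found a mean preoperative STAI of 35.4 (SD 10.0"), sets the difference to detect at one SD (10 points), and states "Necessary power is set at 0.80 and level of significance at 5" per cent. It concludes: "This results in a necessary sample size of 16 participants in each group". Neither the formula nor the sidedness of the test is given.

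**The concern.** Where the primary outcome has also been measured before treatment, adjusting for that measurement removes the part of the between-patient variation that it predicts. In a trial of 32 this is one of the few ways to gain precision without enrolling anyone. The text collects the measurement and then names only tests that ignore it.

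There is little slack to absorb the loss. On the plan's own inputs the t test falls just short of the target power even if every participant supplies the primary STAI. At stake is a modest gain in the chance of detecting a 10-point difference and in the width of the confidence interval. The validity of the comparison is not in question.

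**Working it through.** **Inputs.** From Power and sample size: difference 10, SD 10.0 (so d = 10/10 = 1), power 0.80, significance level 5%, 16 per group. From Randomization: allocation 1:1. From Statistics: unpaired t test or Mann-Whitney test. The correlation r between the recruitment STAI and the primary STAI is not in the documents and is treated below as an assumption.

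**1. Reproducing 16 per group.** Normal approximation: n = 2(z_alpha + z_power)²/d².
- Two-sided: 2 × (1.960 + 0.842)² = 15.70, rounded up to 16. This matches the plan.
- One-sided: 2 × (1.645 + 0.842)² = 12.37, rounded up to 13. This does not match.

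The two-sided reading is therefore inferred from the match; the plan does not state it.

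**2. Power of the unpaired t test.** Noncentral t, df = 2n − 2, noncentrality d√(n/2). At n = 16: df = 30, noncentrality √8 = 2.83.

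| Evaluable per group | Power, two-sided 5% |
|---|---|
| 15 | 0.753 |
| 16 | 0.781 |
| 17 | 0.807 |

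The shortfall at 16 is 0.80 − 0.781 = 0.019. The difference detectable with 80% power at 16 per group is 10.2 points. An SD of 9.77 would close the gap; SDs of 9.5 and 10.5 give power of 0.821 and 0.741. For the Mann-Whitney test at 16 per group, simulation with normal data (40,000 trials) gives about 0.754. That figure depends on the assumed shape of the distribution.

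**3. Power with adjustment for the recruitment STAI.** ANCOVA has df = 2n − 3 and residual SD 10√(1 − r²). The variance of the treatment effect is 100(1 − r²)(2/n) × (1 + t_B²/(2n − 2)), where t_B is the two-sample t statistic for the chance baseline difference. Power is averaged over the distribution of t_B. At n = 16 the mean of the last factor is 1 + (30/28)/30 = 1.036, which is the price of estimating the covariate slope.

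| r (assumed) | Power, 16 per group |
|---|---|
| 0 | 0.766 |
| 0.2 | 0.783 |
| 0.3 | 0.804 |
| 0.4 | 0.834 |
| 0.5 | 0.873 |

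Direct simulation (100,000 trials each) gives 0.766 at r = 0 and 0.804 at r = 0.3. ANCOVA equals the t test (0.781) at r of about 0.19 and reaches 0.80 at r of about 0.28. With 15 evaluable per group, 0.80 needs r of about 0.38. Leaving out the baseline-imbalance factor would give 0.817 at r = 0.3, which is slightly optimistic.

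**4. Rank-based version.** With both scores ranked, n = 16, r = 0.3 and a shift of one SD, simulated power is 0.782 for normal data and 0.876 for an assumed skewed shape (gamma, shape 2). Type I error is 0.051 and 0.050. Rank-based power depends on the distribution, so no single figure should be quoted for it.

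**The case against.** The strongest reply is that nothing here is an error. The normal approximation is conventional, it reproduces the plan's number exactly, and the 1.9-point gap is smaller than the uncertainty in an SD taken from one earlier study. The unadjusted tests are valid in a randomised trial, so a covariate is a matter of efficiency. The gain also rests on a correlation that the documents do not give, with an unstated interval between recruitment and surgery; below about 0.19 adjustment loses power.

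Most of this stands, and it sets the size of the point. The gap in power is only a wording correction. What remains is that the covariate is already collected and that the possible loss from using it is small and bounded (about 1.5 points), while the gain at a moderate correlation is several times larger.

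A reader might infer more than the documents support:
- *That 16 per group is a miscalculation, or that more participants are needed.* It is a standard approximation, narrowly short for the t test.
- *That the planned comparison is biased.* Randomisation protects it.
- *That the trial makes no use of the recruitment STAI, or has no reserve for dropout.* The closing note calls this text an abbreviated translation, so it shows only that neither is mentioned here.

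**Conclusion.** The point holds as a recommendation on precision. The Statistics section of this text names no use of a pre-treatment STAI that the trial collects, and pre-specified adjustment is a low-cost improvement. With 16 evaluable per group, power would move from 0.781 (t test) to about 0.80 at r = 0.3 or 0.87 at r = 0.5, and to 0.766 at r = 0. These figures assume a two-sided 5% test, a 10-point difference, SD 10, approximately normal scores, and correlations that are illustrative only.

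The accompanying correction is minor: on the same inputs, the t test has a type II error of about 22% rather than 20%.

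**What to change.** 1. **Statistics.** Before unblinding, specify: *The primary analysis is an ANCOVA of the STAI 60 minutes before surgery, with treatment as factor and the recruitment STAI as covariate (two-sided 5%). A rank-based analysis with the same covariate is reported in every case as a sensitivity analysis.* The rank-based analysis should not be a replacement triggered by the look of the data, because that would bring back an undefined choice between methods.
2. **Power and sample size.** Restate: *The target power is 0.80. The two-sided normal approximation gives 16 per group; with 16 evaluable per group, an unpaired t test has about 78% power for a 10-point difference with SD 10.*
3. **Correlation.** State the assumed correlation and its basis, with the range: about 0.77 at r = 0, 0.80 at r = 0.3 and 0.87 at r = 0.5, all with 16 per group. Quote no single power figure for the rank-based analysis.

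**Cost.** Wording and one covariate already collected; no added participants or visits. The risk is about 1.5 points of power if the correlation is zero (0.781 − 0.766 = 0.015).
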